2.5.2. Benefit Assessment

Patients with gastroparesis arising from diabetic or idiopathic origin may benefit from receiving NG101, which has the potential to alleviate the significant symptom burden associated with the condition. Use of metopimazine in France has been associated with benefit in the treatment of nausea and vomiting ([Vogalene Summary of Product Characteristics, 2017](#)). In addition, participants may benefit from the clinical monitoring and continuation of background medications during the study.

2.5.3. Overall Benefit: Risk Conclusions

Taking into account the measures taken to minimize risk to participants in this study, the potential risks identified in association with NG101 are justified by the potential benefits that may be afforded to participants with gastroparesis. In France, metopimazine is approved for the symptomatic treatment of nausea and vomiting, and has been prescribed for over 40 years. The body of evidence generated to date reflects a positive benefit risk balance in that indication.

3. Objectives and Endpoints

The following objectives and endpoints are included in this study:

Objectives	Endpoints
Primary	

 To determine the efficacy of NG101 to reduce nausea severity in participants with gastroparesis To evaluate the safety of NG101 in participants with gastroparesis 	
 Change from baseline at Weeks 7 through 12 in the nausea severity score in the Diabetic and Idiopathic Gastroparesis Symptoms daily diary (DIGS-DD). Incidence and severity of treatment-emergent adverse events (TEAEs), treatment-emergent adverse events of special interest (TEAESIs), and treatment-emergent serious adverse events (TESAEs); evaluation of safety laboratory assessments, vital signs, ECG results, and physical examination findings.
Secondary	
Key Secondary Endpoints
 
 Change from baseline at Weeks 7 through 12 in the DIGS-DD: 
 Number of discrete episodes of vomiting Early satiety severity score Post-prandial fullness severity score Abdominal pain severity score Total severity score (nausea, early satiety, post-prandial fullness, abdominal pain) 
Additional Secondary Efficacy Endpoints
 
 Change from baseline at Weeks 7 through 12 in the: 
 Number of hours of nausea per 24-hour period Number of hours of abdominal pain per 24-hour period Change from baseline at Weeks 7 through 12 in the vomiting severity score Percent of nausea-free days Patient Global Impression of Severity (PGI-S) score Patient Global Impression of Change (PGI-C) score


 • To evaluate the PK of NG101 • To evaluate the PD effects of NG101 	
 • Change from baseline to Week 12 in: 
 ◦ Patient Assessment of Upper Gastrointestinal Disorders (PAGI)-Symptoms (SYM) ◦ PAGI- quality of life (QOL) ◦ Total and subscale scores on the Nausea Profile (NP) • Change from baseline through Week 4 in each of the components of the DIGS-DD (nausea, vomiting, early satiety, post-prandial fullness, and abdominal pain) • Change from baseline in gastroparesis symptoms as measured by the Gastroparesis Cardinal Symptom Index daily diary (GCSI-DD) • Change from baseline in weekly Treatment Satisfaction score • Weekly use of rescue medication • PK parameters • Prolactin levels at indicated timepoints

Exploratory
 
 • To evaluate the efficacy of NG101 to reduce the symptom severity of feeling of abdominal fullness and abdominal bloating • To evaluate the efficacy of NG101 to improve the symptom of nausea • Association of exposure and clinical response • Additional analyses of clinical response in gastroparesis symptoms • Healthcare resource utilization • Association of serum glucose with clinical response 	
 • Change from baseline at Weeks 7 through 12 in the feeling of abdominal fullness severity score and in the abdominal bloating severity score • Level of improvement reported on the Nausea Improvement assessment • Association of PK parameters and changes in gastroparesis symptom PRO scores. • Association of PK parameters and safety assessments • Achievement of threshold levels of improvement or worsening in each of the components of the DIGS-DD (nausea, vomiting, early satiety, post-prandial fullness, and abdominal pain) • Composite symptom severity scores • Number of visits to healthcare providers • Association of serum glucose levels and HgbA1c with gastroparesis symptom PRO scores

Abbreviations: DIGS-DD = Diabetic and Idiopathic Gastroparesis Symptoms Daily Diary;
 ECG = electrocardiogram; GCSI-DD = Gastroparesis Cardinal Symptom Index Daily Diary;

PAGI-SYM = Patient Assessment of Upper Gastrointestinal Disorders -Symptoms Questionnaire;
PAGI-QOL = Patient Assessment of Upper Gastrointestinal Disorders -Quality of Life; PGI-C = Patient Global Impression of Change; PGI-S = Patient Global Impression of Severity; PD = pharmacodynamic;
PK = pharmacokinetic; PRO = patient-reported outcomes; TEAEs = treatment-emergent adverse events;
TEAESIs = treatment-emergent adverse events of special interest; TESAEs = treatment-emergent serious adverse events.

4. Study Design

4.1. Overall Design

This is a randomized, double-blind, parallel-group (4 arms), placebo-controlled, multicenter study to evaluate the safety and efficacy of 3 dose levels of NG101 compared with placebo in participants with diabetic or idiopathic gastroparesis.

The total duration of the study for each participant will be approximately 20 weeks. Following a Screening Period of up to 4-weeks, eligible participants will enter a 2-week Pretreatment Period during which time they will complete specified gastroparesis symptom assessments to establish baseline data and to determine compliance with completion of these assessments. Following completion of the Pretreatment Period, a participant's randomization eligibility will be determined (based on all inclusion/exclusion criteria, including the participant's compliance with eDiary completion).

Participants who do not initially meet study screening criteria (ie, are screen failures) may be rescreened (no more than 1 additional Screening) after consultation with and approval by the sponsor. A participant's eligibility for the study must be confirmed by the sponsor's Medical Monitor, or designee, prior to randomization.

Participants eligible for the clinical study will be randomized in a 1:1:1:1 ratio to receive either NG101 treatment arms of 5 mg, 10 mg, or 20 mg, or matching placebo during a 12-week Treatment Period. Randomization will be stratified on the following factors: gastroparesis etiology (diabetes vs idiopathic), sex (male vs female), and current cannabinoid use (yes vs no). Determination of diabetes etiology will be done according to the medical history data at Screening.

NG101 will be administered orally (PO) QID for 12 weeks. The 20 mg arm will initiate dosing on Day 1 with 5 mg QID for 4 days, followed by 10 mg QID for 3 days, and then 20 mg QID through Week 12. No titration will occur in the 5 mg and 10 mg arms. The study drug should be taken by participants approximately 30 minutes before a meal 3 times a day and 30 minutes before bedtime, with a minimum interval of 4 hours between doses.

Two weeks following the end of treatment / Week 12 Visit, participants will return to the clinic for an End of Study (EoS) Visit / Follow-up Visit.

If a participant permanently discontinues study medication (for any reason) prior to the Week 12 Visit, the participant must attend the Early Discontinuation Visit as soon as possible, and then the Safety Follow-up Visit 2 weeks later.

The sponsor will review blinded data on an ongoing basis. Independent reviews of safety data will be done if needed.

Study Assessments:

Study assessments will be performed at the times specified in the Schedule of Activities (SoA – Section 1.3).

The primary efficacy objective is to determine the efficacy of NG101 to reduce nausea severity in participants with gastroparesis. The primary endpoint is the change from baseline at Weeks 7 through 12 for the nausea severity score in the Diabetic and Idiopathic Gastroparesis Symptoms

Daily Diary (DIGS-DD). Key secondary efficacy endpoints will also be assessed by the DIGS-DD and include changes from baseline at Weeks 7 through 12 in the DIGS-DD number of discrete episodes of vomiting, early satiety severity score, post-prandial fullness severity score, abdominal pain severity score, and total severity score (nausea, early satiety, post-prandial fullness, abdominal pain). An eDiary will be used to collect information for the primary and key secondary endpoints.

In addition, blood samples will be obtained to measure plasma levels of metopimazine and metopimazine acid following single-dose administration (Day 1) and at steady-state after multiple-dose administration (Week 2). Blood samples for PK will be collected at the Day 1 and Week 2 visits for all participants (up to 3 hours after the first dose on each occasion. In a subset of participants (8 to 10 participants per treatment arm; 32 to 40 participants total), intensive sampling will be performed (up to 6 hours after the first dose at the Day 1 and Week 2 visits, as well as 1 and 2 hours after the second dose at the Day 1 visit).

4.2. Scientific Rationale for Study Design

Patients with gastroparesis arising from either diabetic or idiopathic etiology will be enrolled in this study. Both subsets of patients may derive improvement in symptoms from D₂ inhibition, and thus treatment with metopimazine. Documentation of delayed gastric emptying is required in order to confirm the diagnosis of gastroparesis. A minimum severity of symptoms is required in order to facilitate demonstration of study drug treatment effect. The 12-week duration of the Treatment Period will enable assessment of the durability of response to treatment with metopimazine.

Dose selection for this study is based on the evaluation of a range of estimated target receptor (D₂) occupancies, phase 1 study results, and the clinical experience with marketed metopimazine in France (see [Section 4.3](#)). The dose escalation in the 20 mg QID treatment arm is included as mitigation against potential OH AEs, and to assess adaptation to alpha-1 receptor inhibition.

The primary endpoint of this study is the change in nausea severity. This endpoint was chosen since nausea is one of the most frequently reported symptoms of gastroparesis, and also has a major impact on patient quality of life ([FDA 2019](#)). Moreover, nausea is likely to be the most sensitive symptom of gastroparesis to facilitate detection of a treatment effect from D₂ inhibition.

A novel PRO tool to assess the signs and symptoms of gastroparesis, the DIGS-DD, is being developed and employed in this study since no qualified assessment tools for gastroparesis currently exist. The DIGS-DD will assess the impact of NG101 on the symptoms of gastroparesis in this study, and results will enable a determination of appropriateness and reliability of the DIGS-DD for use in future potentially pivotal studies.

Rescue medication rules have been designed to balance the need to treat a participant's symptoms and the ability to detect a treatment effect of metopimazine. Stratification factors were identified as potentially impacting the clinical course and/or treatment response, and have been incorporated into planned analyses.

4.2.1. Participant Input into Design

No specific input into the study design was sought from patients directly; however, interviews were conducted with patients with gastroparesis to develop the outcome assessments included in this study.

4.3. Justification for Dose

Nonclinical support for dosing in humans is based on findings from the NG101 animal toxicology studies (13-week studies 1365-18032 [rat] and 1365-18033 [dog]). Results were consistent with the pharmacology of NG101 and the phase 1 safety profile; therefore, the proposed phase 2 doses are considered appropriate.

The sponsor's phase 1 program with metopimazine (Vogalene) and NG101 demonstrated an acceptable safety profile for the doses proposed in phase 2. Single doses up to 60 mg, and multiple doses up to 45 mg Q6H for 5.25 days were administered. Analyses of safety data revealed a trend only for an increased risk of orthostatic changes. Notably, this risk has a clear causative mechanism (alpha receptor inhibition), was dose-dependent, and at doses of 15 and 30 mg the orthostatic hypotension only occurred on Day 1 and only at Hour 1. This pattern of adaptation and reduced risk of orthostasis with continued dosing is consistent with what has previously been reported for alpha receptor inhibition. The top dose of 20 mg QID is expected to have an acceptable safety profile, manageable in a similar way to approved alpha receptor inhibitors (ie, with dose titration).

4.

[REDACTED]

[REDACTED]

[REDACTED]

Dosing will occur approximately 30 minutes before a meal 3 times a day and 30 minutes before bedtime, with a minimum interval of 4 hours between doses. This regimen will provide maximal coverage for participants during and just after meals, when symptoms are reported to be highest. An additional dose will be given before bedtime in order to provide optimal potential efficacy, and potentially minimize morning symptoms.

In accordance with FDA draft guidance ([FDA 2019](#)), treatment duration is 12 weeks. Given that steady-state conditions for metopimazine were achieved by Day 1 of the NG100-101 study, the 30 to 40% accumulation demonstrated on Day 6 represents the extent of accumulation anticipated with the 12 weeks of dosing planned for the study. Treatment for a 12-week duration will allow for a confirmation of the durability of response as well as a quantitative evaluation of the proposed PRO (the DIGS-DD).

4.4. End of Study Definition

A participant is considered to have completed the study if he/she has completed all phases of the study, including the Week 12 visit and the EoS/Safety Follow-up Visit.

The end of the study is defined as the date of the last visit of the last participant in the study.

5. Study Population

Prospective approval of protocol deviations to recruitment and enrollment criteria, also known as protocol waivers or exemptions, is not permitted.

Note: "Enrolled" means a participant, or their legally acceptable representative, agreed to participate in a clinical study following completion of the informed consent process.

5.1. Inclusion Criteria

Participants are eligible to be included in the study only if all of the following criteria apply:

Age

1. Participant must be \geq 18 years of age at the time of signing the informed consent.

Type of Participant and Disease Characteristics

2. Participant has a diagnosis of diabetic or idiopathic gastroparesis with:
 - Documented evidence of no mechanical obstruction, as determined by a gastroenterologist such as by esophagogastroduodenoscopy or upper gastrointestinal series, and in the investigator's opinion there is no current indication of obstruction, *and*
 - Diagnosis and symptoms consistent with gastroparesis (eg, nausea, vomiting, early satiety, post-prandial fullness, and abdominal pain) for at least 6 consecutive months preceding the Screening Visit, *and*
 - Delayed gastric emptying of solids during the Screening Period or within 12 months prior to the Screening Visit as demonstrated on either the US FDA-approved breath test (demonstrating delayed gastric emptying at 4 hours) or scintigraphy (demonstrating \geq 10% residual food remaining at 4 hours).

Note: There must be a minimum of 7 days between the gastric emptying study and the start of the Pretreatment Period, *and*

- No known cause other than diabetes (ie, participants with gastroparesis due to other causes such as surgery, Parkinson's disease, post-abdominal irradiation, atrophic gastritis, suspected arterial occlusion, Crohn's disease, Chagas disease, etc., would be excluded).

Note: A minimum of 120 participants with diabetic gastroparesis and a minimum of 120 participants with idiopathic gastroparesis will be randomized.

3. Participants using a gastric stimulator must have had stable symptoms for at least 3 months prior to the Screening Visit following either:
 - Discontinuation of the gastric stimulator, *or*
 - Initiation of a stable treatment regimen. The participant must agree to maintain the same stable treatment regimen for the duration of the clinical study.

4. Participant must have all of the following during each week of the Pretreatment Period on the DIGS-DD:
 - Sum of the mean severity scores for each of the 4 gastroparesis symptoms ≥ 12 .
(The 4 symptoms are: nausea, early satiety, post-prandial fullness, and abdominal pain.)
 - A mean nausea severity score that is ≥ 4 and also greater than the mean severity score for abdominal pain.

5.2. Exclusion Criteria

Participants are excluded from the study if any of the following criteria apply:

Medical History

1. Participant has another active disorder that, in the opinion of the investigator, can cause abdominal pain or discomfort, nausea, vomiting, fullness, bloating, or other gastrointestinal symptoms that may confound the assessment of gastroparesis symptoms.
2. Participant has been hospitalized within the 2 months prior to the Screening Visit for uncontrolled diabetes mellitus, gastroparesis, or associated malnutrition.
3. Participant has had surgery that meets any of the following criteria:
 - Gastric surgery, including fundoplication, gastric banding, bypass, resection, or gastric per-oral endoscopic pyloromyotomy, at any time before the Screening Visit.
 - Surgery of the abdomen, pelvis, or retroperitoneal structures during the 6 months before the Screening Visit.
 - An appendectomy or cholecystectomy during the 3 months before the Screening Visit.
 - Other major surgery during the 3 months before the Screening Visit.
4. Participant has evidence of unexplained recurrent dizziness or syncope within 6 months prior to the Screening Visit.
5. Participant has a history of intolerance to phlebotomy, (eg, experiences dizziness or syncope).
6. Female participants with a history of galactorrhea, or unexplained amenorrhea.
7. Participant has history of or current clinically significant cardiac arrhythmia, including ventricular tachycardia, ventricular fibrillation, Torsade des Pointes, bradycardia, sinus node dysfunction, heart block, or family history prolonged QT syndrome. Participants with minor forms of ectopy (eg, premature atrial contractions) are not necessarily excluded.
8. Significant CV events (eg, myocardial infarction, unstable angina, hospitalization for congestive heart failure, cardiac surgery, ischemic or hemorrhagic stroke, or transient ischemic attack) within 6 months before the Screening visit.
9. Participant has a history of cancer, including prolactinoma (resected basal cell or squamous cell carcinoma of the skin is acceptable). *Note:* Participants with a history of cancer are eligible provided that the malignancy has been in complete remission

(disappearance of all signs of cancer in response to treatment) for at least 5 years before the Screening Visit.

10. Participant has a history of active alcoholism or drug addiction within 12 months prior to the Screening Visit.
11. Participant engages in daily recreational use of marijuana. *Note:* If participants are currently using marijuana or other cannabinoids, concomitant use is allowed if it is considered stable over the 4 weeks before Screening. Use must not increase during the study. Up to approximately 140 participants can be cannabinoid users (see [Section 9.1](#)), and of these up to approximately 56 can be marijuana users.
12. Urine drug screen positive for non-prescribed drugs, except cannabinoids if use is reported by the participant.
13. Participant engages in vaping.
14. Participant has been hospitalized for a psychiatric condition or has made a suicide attempt within 12 months prior to the Screening Visit.
15. Participant has a history of clinically significant hypersensitivity or allergies to any of the excipients contained in the study medication (NG101 or placebo).
16. Participant has an acute or chronic condition that, in the investigator's opinion or sponsor's opinion, would limit the participant's ability to complete or participate in this clinical study.
17. Participant has a body mass index < 18 kg/m² or > 39 kg/m².

Prior / Concomitant Therapy

18. Participant has had endoscopic pyloric injections of botulinum toxin within the 6 months prior to the Screening Visit.
19. Participant has received and tolerated an adequate course (at least 10 mg administered at least 3 times a day for at least 1 month) of treatment with domperidone and showed no notable symptomatic improvement in gastroparesis symptoms.
20. Use prior to Screening (within the previous 14 days or 7 half-lives, whichever is longer) or intended use during the study of any prohibited medications (see [Appendix 10.2](#)).
21. Initiation of treatment or change in dose or dose regimen within 3 months prior to the Screening Visit for any drug that prolongs QT interval. *Note:* Concomitant use of drugs that prolong QT interval is permitted provided that the participant has been receiving the drug for at least 3 months, has a normal QT interval at the Screening Visit, and remains on same dose and regimen during the clinical study (see [Appendix 10.2](#)).
22. Use of ondansetron or promethazine as an anti-emetic more than 2 times/day (total daily doses should not exceed 16 mg ondansetron or 50 mg promethazine).
23. Use of anti-emetics (ie, ondansetron or promethazine) within 24 hours prior to the Day 1 visit.
24. Participant is receiving parenteral nutrition or using a feeding tube.
25. Change in use of any alternative treatment (eg, acupuncture, hypnosis) from 2 weeks prior to the Screening Visit until the EoS.

26. Changes in dose or dose regimen from 30 days prior to the Screening Visit until the EoS visit for any chronically administered concomitant medications listed in the permitted medications section (see [Appendix 10.2](#)).

Prior / Concurrent Clinical Study Experience

27. Current enrollment or past participation within the last 30 days before signing of consent in any other clinical study involving an investigational study treatment or device or is planning to receive another investigational intervention at any time during the study (see [Appendix 10.2](#)).

Diagnostic Assessments

28. Participant has uncontrolled diabetes defined as HgbA1c > 10% at the Screening Visit.
29. Participant has thyroid stimulating hormone (TSH) below the lower limit of normal, or above the upper limit of normal (ULN) if free T4 is below the lower limit of normal.
30. Male participants with serum testosterone below the lower limit of normal at Screening.
31. Participant has prolactin levels > 2 x ULN
32. Participant has QTcF > 450 msec for male participants or QTcF > 470 msec for female participants, or QTcF > 480 msec in participants with right bundle branch block (participants with left bundle branch block are excluded).
33. Participant experiences any clinically significant finding on a physical exam, 12-lead ECG, or clinical laboratory test after signing the ICF but prior to randomization. The investigator will determine if a particular finding is clinically significant. In making this determination, the investigator will consider whether the particular finding could prevent the participant from performing any of the protocol-specified assessments, could represent a condition that would exclude the participant from the study, could represent a safety concern if the participant continues in the study, or could confound the study-specified assessments of safety or efficacy.
Note: By definition, a positive drug screen is clinically significant (with the exception of marijuana).
34. Participant has severe postural symptoms and/or absolute systolic BP < 90 mm Hg upon standing. *Note:* these severe symptoms include presyncope, syncope, and other severe AEs that are considered of substantial clinical relevance by the investigator (see [Table 3](#) for additional details and definitions).
35. Estimated glomerular filtration rate \leq 45 mL/minute/1.73 m² (based on the Chronic Kidney Disease Epidemiology Collaboration [CKD-EPI] equation; see [Appendix 10.7](#)).
36. Aspartate aminotransferase or alanine aminotransferase > 2 x ULN; alkaline phosphatase or bilirubin >1.5 x ULN (isolated bilirubin >1.5 x ULN is acceptable if bilirubin is fractionated and direct bilirubin < 35%).

Other Exclusions

37. Donation of blood or blood loss > 400 mL within 90 days prior to the Screening Visit.

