2.2.1.2. Study NG101-102 (Comparative PK Study)

Study Design

Study NG101-102 was a phase 1 two-cohort, partial crossover, open-label, randomized, single-dose study to assess the relative bioavailability between NG101 (metopimazine mesylate) and the reference metopimazine formulation (Vogalene) in healthy participants at a single study center in France. The NG101 dose (15 mg) for Cohort 2 of the study was determined from the PK results from Cohort 1 of the study. The reference metopimazine was administered either orally as a 15 mg capsule or via a diluted intravenous (IV) infusion of a 10 mg/mL solution administered as 7.5 mg over 60 minutes.

Cohort 1 was a 3-period, partial crossover in the fasted state with 3 administrations of NG101 7.5 mg PO, Vogalene 15 mg PO, or Vogalene 7.5 mg IV. There was a wash-out period of 48 hours between each administration. A total of 8 participants were enrolled and received each of the 3 treatments.

Cohort 2 was a 3-period, cross-over design with 3 administrations of 15 mg of each of the following: oral formulation of NG101 fasting, oral formulation of NG101 after a high-fat breakfast, oral formulation of the reference metopimazine fasting. There was a wash-out period of 48 hours between each administration. Fifteen participants were enrolled and received each of the 3 treatments.

Results

Relative Bioavailability and Food Effect

Based upon geometric least squares mean ratio, preliminary estimates of the relative bioavailability of NG101 compared to Vogalene, each under fasting conditions, were 109% for AUC_{last} and 86.4% for C_{max} , but the 90% confidence intervals (CIs) were too wide to conclude equivalence. A high degree of inter-subject variability was observed for these PK parameters and several participants had plasma concentrations below the limit of quantification (5 ng/mL) within the first 6 hours after dosing. An elimination $t_{1/2}$ for metopimazine could not be determined for any participant; therefore, AUC_{0-inf} could not be calculated. Given that the time of last measurable plasma metopimazine concentration varied within participants for the different study treatments, an additional exploratory PK in which AUC_{last} was uniformly truncated at the time of last measurable concentration showed a relative bioavailability of 98%. For metopimazine acid, the 2 formulations met bioequivalence criteria with geometric mean ratios of 92.2% and 93.1% for AUC_{last} and C_{max} respectively.

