2.4. Background

Gastroparesis is a chronic disorder of the stomach characterized by delayed gastric emptying without evidence of mechanical obstruction (Camilleri et al. 2013; Stein et al. 2015). The core set of symptoms of gastroparesis include nausea, vomiting, early satiety, post-prandial fullness, and abdominal pain (Food and Drug Administration [FDA] 2019; Camilleri et al. 2013). The most common etiologies of gastroparesis are of idiopathic and diabetic origin (Parkman 2018; Camilleri et al. 2013). While the overall incidence of gastroparesis is not well understood, the 10-year incidence in Olmsted County Minnesota, United States (US), was 5.2% in patients with type 1 diabetes, 1% in patients with type 2 diabetes, and 0.2% among non-diabetic controls (Choung et al. 2012). Evidence suggests gastroparesis is associated with increased healthcare costs, including an increased frequency of hospitalizations (Wadhwa et al. 2017;

[Camilleri et al. 2013](#)). Overall, gastroparesis adversely affects the lives of patients, and there is urgent need to develop treatments with a favorable risk-benefit profile.

Neurogastrx, Inc. is developing NG101, a mesylate salt of metopimazine, a potent and selective, peripherally-restricted (ie, very limited ability to penetrate the brain), hERG negative (ie, no hERG inhibition at expected human plasma exposures), dopamine D₂/D₃ receptor antagonist for the treatment of gastroparesis. Metopimazine (oral capsules, orally disintegrating tablet, suppositories, liquid drops or syrup) has been approved in France for over 40 years under the current trade name Vogalene[®] (15 mg oral capsule; 7.5 mg orally disintegrating tablet) for the short-term symptomatic treatment of nausea and vomiting. An IV formulation (10 mg) is approved and is almost exclusively used for the treatment of chemotherapy-induced nausea and vomiting in adults and children. The vast majority of prescriptions for adults and infants / children are for seasonal gastroenteritis or acute nausea and vomiting of various etiologies. Metopimazine is also available as an over-the-counter medication (Vogalib[®], 7.5 mg orally disintegrating tablets).

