Dopamine antagonism has been well validated as an effective treatment for gastroparesis. Metoclopramide and domperidone, existing D₂ antagonists, have gastroprotective properties as well as anti-nausea/anti-emetic effects. However, these agents are associated with limiting CNS and CV side effects, respectively. Although metopimazine belongs to the chemical family of phenothiazines (most of which are associated with CNS and/or CV side effects), its use is rarely associated with CNS side effects, and has not been associated with significant cardiac risk when used at the current marketed doses in France. As such, NG101 is a promising candidate for the treatment of gastroparesis.

A detailed description of the chemistry, pharmacology, efficacy, and safety of metopimazine is provided in the NG101 IB.

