Extrapyramidal symptoms (EPS)	EPS is associated with centrally acting dopamine blockade. NG101 has low penetration of the blood brain barrier, and thus low risk for EPS.	Clinical assessment for EPS.
Study Procedures		
Minimal risk from blood draws.	Blood draws are standard procedures in clinical trials.	Standard techniques.
Other		
No other known risks.		

Abbreviations: AE = adverse event; BP = blood pressure; CNS = central nervous system; EPS = extrapyramidal symptoms; NMS = neuroleptic malignant syndrome; OH = orthostatic hypotension; QID = 4 times daily; T_{max} = time of maximum concentration.

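### Exclusion criterion 15 covers allergy to the excipients only; a known allergy to metopimazine, the drug under test, is left to discretion

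*Combined protocol and SAP*

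**What the plan says.** Section 5.2, criterion 15, gives the study's only allergy exclusion: "Participant has a history of clinically significant hypersensitivity or allergies to any of the excipients contained in the study medication (NG101 or placebo"). The product is identified in Section 2.4 as "NG101, a mesylate salt of metopimazine", and Section 2.2.1.2 and Table 1 in Section 6.1 agree.

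Two other provisions bear on the point:

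- Criterion 16 excludes a person with an acute or chronic condition that, in the opinion of the investigator or the sponsor, would limit the person's "ability to complete or participate in this clinical study".
- Section 4.1 requires eligibility to be confirmed by the sponsor's "Medical Monitor, or designee, prior to randomization".

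**The concern.** The parenthesis in criterion 15 says whose excipients are meant, those of the active capsule and those of the placebo capsule. It does not bring in the active substance. Read literally, the rule excludes someone allergic to a capsule ingredient and is silent on someone allergic to metopimazine.

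The stake is participant safety. A person with a known, clinically significant allergy to the drug could be randomised and, in three of the four arms, take it four times a day for 12 weeks. Prior exposure is possible: Section 2.4 describes more than 40 years of approved use in France and notes that "Metopimazine is also available as an over-the-counter medication". The countries of recruitment are not stated.

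**Working it through.** The plan states no figure on this point, so the check is mainly one of reading. Each place that could close the gap was compared with criterion 15.

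| Place | What it covers | Names allergy to metopimazine? |
|---|---|---|
| Section 5.2, criterion 15 | Allergy to excipients of NG101 or placebo | No |
| Section 5.2, criterion 16 | Limiting condition, by opinion | No |
| Section 5.2, criterion 20, with Appendix 10.2 | Recent or intended use of listed drugs | No; concerns use, not past reactions |
| Section 5.2, criterion 33 | Significant examination, ECG or laboratory findings between consent and randomisation | No; not drug-allergy history |
| Remaining exclusions and the 10 inclusions | Other matters | No |
| Section 2.5.1 risk table | Orthostatic hypotension, NMS, prolactin effects, EPS | No |
| Section 8.5.7, Table 3 | Adverse events of special interest | No |
| Section 8.2 | Contraindications to the breath test (Spirulina, egg, milk, wheat) | No; unrelated to study drug |
| Section 4.1 | Medical Monitor confirms eligibility | No; adds no criterion |
| Section 1.3, medical history | Includes prior gastroparesis treatments | No; may reveal an allergy without making it disqualifying |

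The express allergy exclusions are therefore 1 of 37, and that one stops at the excipients.

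The size can only be illustrated. Allocation is 1:1:1:1 with three active arms, so for anyone randomised

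P(metopimazine) = 3/4 = 0.75.

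Let k be the number of people with a known metopimazine allergy among the 280 randomised. The expected number on active drug is 0.75 × k. The range k = 0 to 2 is an assumption; nothing in the documents supports a particular value.

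| k (assumed) | k / 280 | Expected on active drug |
|---|---|---|
| 0 | 0% | 0 |
| 1 | 0.36% | 0.75 |
| 2 | 0.71% | 1.5 |

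These figures count people who have already been randomised, that is, people whom the discretionary checks did not stop.

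**The case against.** The strongest reply is that criterion 16 is itself a written exclusion, that the opinion of either the investigator or the sponsor is enough to invoke it, and that the Medical Monitor must then agree before randomisation. For an allergic person to be dosed, both would have to see a known allergy to the test drug and find no obstacle. A careful investigator would be expected to exclude such a person. The group is also likely to be tiny, since a known allergy normally needs earlier exposure and the marketing described is French. The first dose is taken in the clinic with 3 hours of observation. The Investigator's Brochure, which is not among the documents, may hold a contraindication.

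Most of this stands, and it sets the weight of the point. The hazard is low, the range of 0 to 2 is not evidence, and the group's rarity is itself an inference because the recruitment countries are not given. Two further arguments for the concern add little. The entry "No other known risks" in Section 2.5.1 falls under a separate heading for other risks and says nothing about drug allergy. The bar on waivers in Section 5 does not oblige anyone to enrol a person who raises a safety concern.

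What does not stand is that discretion makes the wording adequate. Criterion 16 is framed around a condition that limits participation, and a past drug reaction in someone otherwise well fits that awkwardly. The Medical Monitor's check applies the criteria as written. The Day 1 observation is there for orthostatic hypotension, and most later doses are taken at home. The sponsor chose to write an allergy rule, and that rule omits the ingredient under test.

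**Conclusion.** The concern holds as a minor participant-safety correction. Criterion 15 has the wrong scope, and nothing else in the protocol expressly excludes a known allergy to metopimazine. What is shown is an omission in the eligibility text, not the absence of every safeguard. Few people, perhaps none, would be affected: 0 to 1.5 expected on active drug if 0 to 2 such people were randomised, which is an assumption. The sample size, power, error rate and analysis are untouched.

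**What to change.** In criterion 15, insert the words *metopimazine or to* immediately before the reference to the excipients, and leave the rest of the sentence as it is.

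The sponsor's medical team should also decide whether to extend the criterion to other phenothiazines, since "metopimazine belongs to the chemical family of phenothiazines". The documents contain no cross-reactivity data, so this review does not recommend either course.

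The cost is a few words at the next amendment. Under the same assumption, 0 to 2 candidates would be lost, and they can be replaced within the planned 280. That estimate does not cover an extension to other phenothiazines, which could exclude more people.
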